1.0 Objectives / Specific Aims

We intend to demonstrate that non-invasive, peripheral vascular occlusion increases blood pressure in the conserved vasculature in healthy humans. Data from this study will provide proof of concept for the development of a novel device to improve cardiopulmonary resuscitation (CPR) outcomes during non-traumatic cardiac arrest. We hypothesize that peripheral vascular occlusion of non-vital vascular beds (the lower extremities) will increase blood flow to the more vital organs, the heart and the brain, leading to an improvement in survival and neurologic recovery after cardiac arrest as these outcomes are dependent on heart and brain ischemic injury. By using commercially available, FDA-approved, tourniquets on healthy humans to measure blood pressure with peripheral vascular occlusion, we will be testing our hypothesis in the safest way. We also will demonstrate no substantial change in heart rate.

2.0 Background

For decades, the fields of trauma, orthopedics, and cardiology have utilized vascular occlusion devices for either hemorrhage control or to increase central pressure.¹⁻³ Due to their success in maintaining blood flow proximally during shock scenarios, vascular occlusion devices have increasingly been studied during non-traumatic cardiac arrests. There have been nine preclinical studies in animals that have demonstrated endovascular balloon occlusion devices significantly increase coronary artery blood flow and pressure during cardiac arrest.⁴⁻¹¹ Tourniquets are an external, non-invasive strategy to obtain the same end goal of vascular occlusion and are currently used daily in clinical practice for traumatic wounds and extremity surgery. They have been well studied in civilian and military research for their safety and efficacy, but their use as a CPR adjunct has yet to be realized.¹²⁻¹⁴

Rationale: To our knowledge, blood flow or pressure to vascular beds supplying vital organs (i.e., brain, heart) has not been measured in healthy adult subjects following administration of a non-invasive peripheral vascular occlusion device. This proof-of-concept data is necessary for future development and hypothesis testing for novel CPR adjuncts, which could improve survival and neurologic recovery following cardiac arrest.

2.0 Intervention to be studied

The fluid dynamics Hagen-Poiseuille Equation demonstrates in physical law why peripheral vasoconstriction increases the flow in conserved vascular networks. The Hagen-Poiseuille Equation ($Q = \Delta P \pi r^4 / 8 \eta L$) gives the volumetric flow rate (Q) in a cylindrical tube as it relates to the viscosity of the fluid (η), length of the system (L), radius of the tube (r), and pressure gradient across the tubing (ΔP). Tourniquets placed on the legs would decrease the length of the system (L), thereby increasing the flow (Q) as these variables are inversely proportional. While this equation is an obvious oversimplification, we find it models our expectant results and confirms what we intuitively and anecdotally have noted in our patients. Beyond theory, studies in large animal models and clinical trials offer additional proof of concept.^{4,12-13,15-19} Pigs receiving tourniquet-assisted CPR experienced significantly increased coronary blood flow,

carotid artery pressure, systolic and diastolic blood pressure, end-tidal carbon dioxide, and survival than controls.¹⁷

In order to complete our hypothesis testing safely, we plan to deploy well-studied and FDA approved combat application tourniquets (CAT) on both thighs of volunteer healthy adult subjects while measuring blood pressure in the upper extremities. Research participants in this study will have their blood pressure measured in their upper extremities before and after tourniquet administration in order to serve as within subject controls. The tourniquets will be deployed for no longer than 5 minutes for each of the three repetitions. After the removal of the tourniquets, the participants will be allowed to rest for 3-5 minutes before the next application of the tourniquet.

CAT tourniquets were developed in 2005 by Mark Esposito et al. (US Patent numbers 7,842,067 and 7,892,253) and soon after obtained FDA approval. CAT tourniquets have been indicated for use in emergency situations revolving around a wounded limb, such as hemorrhage control.²²⁻²³ CAT tourniquets are the official tourniquet of the US Army since in 2005.

4.0 Study Endpoints (if applicable)

- **Primary Study Endpoint:** A cardiac arrest porcine model that utilized an intra-aortic balloon catheter for occlusion of the aorta at the level of the diaphragm demonstrated a mean increase in systolic pressure of 17mmHg.¹⁸ Extrapolating from this data to our more distal point of occlusion at the lower extremities, we define the primary study endpoint as successful application of CAT tourniquets in normal physiology in healthy humans with a minimum increase in blood pressure of 10 mmHg measured in the arms. Another primary endpoint is demonstrating no significant change in participant heart rate.
- **Primary Safety Endpoint:** The most common complications following application of a CAT tourniquet is pain or discomfort at the site of tourniquet application. This usually occurs at the edges of the tourniquet due to the increased pressure gradient. Symptoms are typically transient resulting in mild to moderate pain. In order to increase safety of the study and reduce the likelihood of complications, the tourniquet will be tightened to the minimum pressure needed to occlude blood flow to the lower extremities and will be removed after 5 minutes since injury usually occurs 30-60 minutes following tourniquet application²⁰. If any of the subjects report intolerable pain during the study, their participation will be ended immediately.
- **Secondary Safety Endpoints:** There are no secondary safety endpoints.

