6.0 Number of Subjects

- A total of 30 healthy volunteered adults (15 males and 15 females) will be used for our study.
- A power analysis was conducted to determine appropriate sample sizes based on previous data examining hemodynamics following tourniquet application on the lower extremities²¹. Based on a power of 0.8 and an alpha of 0.05, a sample size of 24 participants will be needed for our study. Allowing for post hoc analysis and individual data exclusion if warranted, a total of 30 volunteer research participants will be recruited to partake in the study.

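### Does leaving the role of the 10 mmHg rise unstated undermine the primary endpoint or the stated 80% power?

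*Protocol*

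**What the plan says.** Section 4.0 (Study Endpoints) cites a porcine cardiac arrest model with aortic occlusion that "demonstrated a mean increase in systolic pressure of 17mmHg". It then reasons "Extrapolating from this data to our more distal point of occlusion at the lower extremities" and defines primary success as tourniquet application "with a minimum increase in blood pressure of 10 mmHg measured in the arms". The pressure component is named for the pig result but not repeated in the endpoint clause.

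Section 6.0 (Number of Subjects) says the power analysis was "based on previous data examining hemodynamics following tourniquet application on the lower extremities", a different source from the pig study. It reports: "Based on a power of 0.8 and an alpha of 0.05, a sample size of 24 participants will be needed for our study". To allow for exclusions and post hoc work, "a total of 30 volunteer research participants will be recruited to partake in the study". No difference, SD, test or sidedness is given, and 10 mmHg is not mentioned.

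The section on the intervention makes the comparison a paired one: pressures are taken "before and after tourniquet administration in order to serve as within subject controls".

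**The concern.** A mean goes into the reasoning in section 4.0 and a minimum comes out. The number 10 could play four parts:

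- (a) a threshold for the observed mean change;
- (b) a null value that the confidence interval must clear;
- (c) the difference planned for in a test against zero;
- (d) a responder cut-off for each participant.

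These can give different verdicts on the same data. Take an observed mean rise of 8 mmHg with an assumed SD of 15 in 24 people: t = 8/(15/√24) = 8/3.06 = 2.61, against a two-sided 5% critical value of 2.07 on 23 degrees of freedom. That succeeds against zero and fails under (a) and (b).

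There is also a worry about power. If 10 mmHg is the rise expected from leg occlusion, it cannot also be a minimum that is met with 80% probability. A reader might take the 80% in section 6.0 as the chance of meeting the section 4.0 criterion, and for a primary endpoint that would matter.

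**Working it through.** **Inputs.** From the protocol: 10 mmHg and 17 mmHg (section 4.0); power 0.8, alpha 0.05, N = 24, 30 recruited (section 6.0); paired design (section on the intervention). Assumed, because the protocol gives none: SD of the within-participant change of 10, 15 or 20 mmHg, and normal changes.

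**Reproducing N = 24.** This cannot be done forward, since no difference or SD is stated. Solving backward for a paired comparison:

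- Normal approximation, two-sided: (1.960 + 0.842)/√24 = 0.572 SD units.
- Paired t-test (noncentral t): 0.597 two-sided, 0.523 one-sided.
- If the planning difference were 10 mmHg, the implied SD is 10/0.597 ≈ 16.7 mmHg (two-sided) or 10/0.523 = 19.1 mmHg (one-sided).
- At N = 30, two-sided, the value is 0.529, so 80% power holds up to an SD of 10/0.529 = 18.9 mmHg.

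**Chance of success by role.** With μ the true mean rise:

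- (a) 1 − Φ((10 − μ)/(SD/√n))
- (b) noncentral t with shift (μ − 10)/SD, lower limit of the two-sided 95% interval above 10
- (c) noncentral t with shift μ/SD, two-sided test against zero

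Example for (a), μ = 17, SD 15, n = 24: 7/3.06 = 2.29, so Φ = 0.989.

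| True mean rise, N = 24 | Role | SD 10 | SD 15 | SD 20 |
|---|---|---|---|---|
| 10 | (a) | 50% | 50% | 50% |
| 10 | (b) | 2.5% | 2.5% | 2.5% |
| 10 | (c) | 99.7% | 88% | 65% |
| 17 | (a) | >99.9% | 99% | 96% |
| 17 | (b) | 91% | 59% | 38% |
| 17 | (c) | >99.9% | >99.9% | 98% |

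For (d), half the participants reach 10 mmHg when the mean is 10. At a mean of 17 the shares are 76%, 68% and 64% for SD 10, 15 and 20. No required share is stated.

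**What the table shows.**

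- The 50% and 2.5% entries hold for any trial. A true mean equal to the threshold passes half the time, and a true mean equal to the null value passes at alpha/2. They apply here only if 10 is the expected rise, and section 4.0 does not say so. It calls 10 a minimum, which can equally be a floor set below an unstated expectation.
- If the expected rise is above 10, role (a) reaches 80% at 10 + 0.842 × SD/√24 = 10 + 0.17 SD. That is 11.7 to 13.4 mmHg for SD 10 to 20, all below the pig figure of 17.
- Role (b) is more demanding. It needs 10 + 0.597 SD, or 16.0 to 21.9 mmHg over the same SDs.

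**Setting the two sections side by side.** Section 6.0 attaches power and alpha to haemodynamic data from leg tourniquets, not to the pig extrapolation. An alpha does not belong to role (a), which involves no test. The aim in section 1.0 is to show that pressure rises, and the design is paired. Both point to a test against zero, and the implied SD of 16.7 mmHg lies within the assumed range. This does not prove role (c), but it shows that the stated power and the ordinary reading are compatible.

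**The case for a change.** The best case for a change is that a primary success criterion should be fixed before data are seen, and that this one is worded in the protocol itself and so is not simply left to an analysis plan. The component is not named, nor is the level at which the minimum applies, and the verdict can depend on the choice, as the 8 mmHg example shows. Clarifying it would take about one sentence in each section, from a calculation the protocol says was done.

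Much of this stands. The clause is loose, systolic pressure has to be inferred from the sentence before it, and the literal per-participant reading is open. A clarification would be welcome.

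The link to power does not stand. Fixing the role of 10 mmHg would not make N = 24 traceable, because section 6.0 also omits the difference, SD, test and sidedness and rests on other data. These are two separate silences, and they do not contradict each other. Whether the benchmark is judged by a point estimate or a confidence limit is a decision rule that an analysis plan commonly settles, and one may exist that is not shown.

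**Conclusion.** No change to the plan follows. The protocol leaves out detail, but nothing it states is shown to be wrong: N = 24 is neither reproduced nor refuted, and section 6.0 makes no claim of 80% power for a 10 mmHg minimum. The gap can be filled sensibly by testing the mean paired change in systolic pressure against zero and reading the estimate and its confidence interval against 10 mmHg. A reader can then apply any of the mean-based readings.

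On that reading, and if the true rise is 10 mmHg, two-sided power is at least 80% for an SD of the changes up to about 16.7 mmHg with 24 participants and 18.9 mmHg with the 30 to be recruited. At an SD of 20 it falls to 65% and 75%. These SDs are assumptions, so the figures are illustrative. The conclusion would differ if the protocol had stated that 10 mmHg is the expected rise and also a threshold to be met with 80% power. It states neither.

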10.0 Study Design / Methods

After expressing interest in the study, participants will be asked to come to MUSC for the study visit. On the day of the study, each volunteer will be taken to a private room by IRB approved personnel and consented in person through a signed written consent form. They will be asked to confirm their eligibility in the study based on the inclusion/exclusion criteria. Their blood pressure in their upper extremity will be taken to ensure that it is not elevated on the day of the study (must not be $>130/80$ mmHg). Their responses and blood pressure will be documented. Once the participants have consented to the study, they will have their height and weight recorded. Then, each participant will have their blood pressure measured in each arm by an automated sphygmomanometer while lying down on a medical bench. The blood pressures and the heart rate will be recorded by IRB approved personnel. This will allow each research participant to act as their own control for the experimental procedure. Then, one CAT tourniquet will be placed around each thigh and tightened until no pulse can be felt in the lower extremity. Blood pressure measurements will be repeated in each arm once the tourniquets are secured. Once these blood pressures are documented, the tourniquets will be removed. The maximum time the tourniquets will be applied is 5 minutes to ensure ample time for blood pressure recording. If the measurement cannot be taken within the time frame, the tourniquets will be released. The participants will rest 3-5 minutes between each repetition of the tourniquet application. The whole process will be repeated three times for data validity. CAT tourniquets have been extensively studied for safety, and no long-term consequences or complications have been noted for up to two hours of continuous use. This team will prioritize the safety and comfort of the participant and will limit the tourniquet application time to a maximum of 5 minutes. We will be using the FDA-approved Combat Application Tourniquet (CAT) tourniquet (North American Rescue, Greer, South Carolina, USA). After the data is collected, a debrief session will be conducted, allowing for additional subject monitoring after removal of the tourniquets. During the debrief session, the participant will be asked to lay down or sit in a relaxed position for 5 minutes or until they feel that their leg function is back to baseline. If there is any concern from the participant, the PI or IRB-approved personnel who are medical doctors, will conduct an evaluation. If any of the safety endpoints are noted, it will be recorded, and the participant will be taken to the emergency room for full examination and work-up. The PI or IRB-approved personnel will follow-up with the participant remotely until the safety concern is resolved.

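### The heart-rate primary endpoint promises to demonstrate no change but sets no margin in bpm, so the planned criterion cannot support that conclusion

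*Protocol*

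**What the plan says.** Section 4.0 (Study Endpoints) lists heart rate as a second primary endpoint: "Another primary endpoint is demonstrating no significant change in participant heart rate". Section 1.0 (Objectives) words the same aim differently: "We also will demonstrate no substantial change in heart rate". Neither section, nor any other part of the protocol, gives a limit in bpm, an equivalence margin, a confidence-interval rule or a definition of either adjective.

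The blood-pressure endpoint in Section 4.0 does carry a number: success is tied to tourniquet application "with a minimum increase in blood pressure of 10 mmHg measured in the arms".

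Section 6.0 gives the sample size: "Based on a power of 0.8 and an alpha of 0.05", "a sample size of 24 participants will be needed for our study", and "a total of 30 volunteer research participants will be recruited to partake in the study". It names no endpoint, effect size or SD, and mentions neither heart rate nor equivalence. The design is within-participant. Section 10.0 says of the baseline readings: "This will allow each research participant to act as their own control for the experimental procedure". It repeats the procedure three times per person.

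**The concern.** The wording can be read in two ways, and each needs a margin that is not there.

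1. **As a test result.** The endpoint is met if a paired test of zero change is non-significant. Failing to reject zero does not demonstrate that the change is zero or small. The criterion also rewards imprecision: the smaller or noisier the study, the easier it is to succeed.
2. **As a clinical judgement.** The endpoint is met if the change is not important. The protocol then states no size that separates success from failure. Unless a limit is fixed somewhere in advance, the call is made with the data in view.

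The shift from one adjective in Section 1.0 to another in Section 4.0 leaves it unclear which reading is meant. At stake is one of the two primary conclusions. On the test reading, the verdict depends on how precise the readings are as well as on how far heart rate moved.

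**Working it through.** **The plan's own figure.** The 24 participants in Section 6.0 cannot be reproduced, because the effect size, SD and sidedness are not given. Back-solving a paired t-test at 80% power and alpha 0.05, n = 24 corresponds to a standardised change of 0.60 (two-sided) or 0.52 (one-sided). This neither confirms nor refutes 24, and it says nothing about heart rate.

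**Inputs.** From the protocol: n = 30 recruited, n = 24 needed, alpha 0.05, paired design. Assumed: a two-sided test, and an SD of each participant's mean heart-rate change between 4 and 10 bpm. Averaging three repetitions would lower the SD, so low values are included. The shifts of 2 and 5 bpm and the margins of 3 and 5 bpm are illustrations.

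**Step 1: a real shift passes as no change.** Under a true shift d, the paired t statistic is noncentral t with n − 1 degrees of freedom and noncentrality d√n / SD. The endpoint is met when |t| is below the critical value (2.045 at n = 30, 2.069 at n = 24). For d = 5, n = 30, SD = 8, the noncentrality is 5 × 5.477 / 8 = 3.42, and P(|t| < 2.045) = 0.089.

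| SD (bpm) | 5 bpm shift passes, n = 30 | 5 bpm shift passes, n = 24 |
|---|---|---|
| 5 | 0.0004 | 0.003 |
| 6 | 0.007 | 0.026 |
| 8 | 0.089 | 0.166 |
| 10 | 0.246 | 0.350 |

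**Step 2: the criterion rewards a smaller study.** With SD 10 and a true 5 bpm shift, the probability of success is 0.83 at n = 6, 0.65 at n = 12, 0.35 at n = 24, 0.25 at n = 30 and 0.001 at n = 100.

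**Step 3: the opposite error.** At n = 30 and SD 5, the smallest observed mean change that reaches significance is 2.045 × 5 / 5.477 = 1.87 bpm. A true 2 bpm shift is significant, so fails the endpoint, with probability 0.75, 0.56, 0.42, 0.26 or 0.18 at SD 4, 5, 6, 8 or 10.

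**Step 4: an equivalence rule.** Conclude no substantial change only if mean ± t(0.95, n − 1) × s / √n lies inside ±M; this is two one-sided tests at 0.05. Power was obtained by integrating over the distribution of the sample SD. For M = 5:

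| True change | SD (bpm) | Passes, n = 30 | Passes, n = 24 |
|---|---|---|---|
| 0 | 6 | 0.995 | 0.979 |
| 0 | 8 | 0.910 | 0.815 |
| 0 | 10 | 0.697 | 0.536 |
| 2 | 4 | 0.991 | not computed |
| 2 | 5 | 0.941 | not computed |
| 2 | 6 | 0.848 | not computed |

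A true 5 bpm shift passes at most 5% of the time. With a true change of 0 and n = 30, 80% power holds up to an SD of about 9.1 for M = 5 and about 5.5 for M = 3. Beyond those limits, SD 10 with M = 5 needs 36 participants, and SD 8 with M = 3 needs 63.

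**The case against.** The strongest reply is that only the protocol is at hand. A test, an interval rule or a definition of the adjective may sit in an unseen SAP, and Section 4.0 names no test. The word used in Section 1.0 points to size rather than to a p-value. It is true that a SAP could fix a limit in advance, so it cannot be said that the judgement will certainly follow the data. But the protocol itself makes demonstrating no change a primary endpoint. What counts as success belongs with the endpoint, as it does for blood pressure in the same section. A SAP that applied the wording literally would carry the fault forward.

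The second reply is that the harm is hypothetical and mostly small. This largely stands. At n = 30 a 5 bpm shift is missed less than 10% of the time up to SD 8, and nothing in the protocol supports a particular SD. The two errors also do not occur together: at SD 5 the 5 bpm miss is 0.0004, and at SD 10 the 2 bpm failure is only 0.18. The figures show that the verdict follows precision. They do not show that 30 participants are too few.

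The third reply is that equivalence looks weaker if exclusions leave 24 for analysis. That is correct and is a real cost of the claim.

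Finally, Section 10.0 mentions heart rate explicitly only with the readings before the tourniquets. A reading during occlusion is needed for this endpoint under any analysis, so it is not a cost of the change proposed here.

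**Conclusion.** The concern holds. As written, the heart-rate primary endpoint has no criterion that could support its conclusion, on either reading of the text. That conclusion rests on logic and on the absence of a margin, not on any assumed SD. The practical size does depend on the SD, which the protocol does not give. At n = 30, the chance of passing a true 5 bpm shift is negligible at SD 5 to 6, about 9% at SD 8 and about 25% at SD 10. At SD 5 or below, a 2 bpm shift would fail the endpoint more often than not. The point should be fixed before data collection. It does not touch the blood-pressure endpoint.

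**What to change.** In Sections 1.0 and 4.0, use one wording. For example: no substantial change in heart rate is concluded only if the 90% confidence interval for the mean within-participant change, averaged over the repetitions, lies inside ±M bpm. The sponsor should state and justify M before data collection, and give the power at 30 participants and at 24 in case of exclusions, with the SD assumed. Section 10.0 should say explicitly that heart rate is recorded during occlusion in each repetition.

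If no margin can be justified, or the power is inadequate, report the mean heart-rate change with its 95% confidence interval descriptively and remove the claim of demonstrating no change from both sections.

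The cost is wording; no extra participants are proposed, and no procedure beyond the heart-rate reading that the endpoint already needs. The downside is that an equivalence claim may fail even when heart rate does not change. Above the SD limits shown in the working (about 9.1 bpm for ±5, about 5.5 bpm for ±3, at n = 30), the descriptive option is the one that fits the planned size.
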